12.2 Sample Size Considerations

Primary sample size considerations focused on primary hypothesis 1, testing for a difference in the percentage of children with new caries at 24 months in those randomized to OHT vs. CWT. Sample size was calculated for the chi-square test comparing these two independent percentages, testing at the two-tailed alpha (Type I error rate) of 0.05 level and achieving 80% power (0.20 Type II error rate).

No interim analyses are planned.

Power calculations assumed an underlying new caries incidence at 24 months of 23.8% in the CWT group vs. 14.3% in the OHT group (corresponding to an odds ratio of 0.53; justification given below).

Based on our experience in the pilot study and our previous studies (e.g., the recently completed OHAPH trial), we anticipate examining 70% of enrolled parent/child dyads at 24

months. We do not anticipate missing data other than that due to loss-to-follow-up. We will attempt to follow and include all parents in the analysis regardless of their compliance with the study protocol and level of engagement with the OHT or CWT intervention ('intent to treat'). Parents lost to follow-up will not be replaced. Participants, can, however, become ineligible after randomization (and not evaluable), for example, if a parent loses custody of the child. Participants who become ineligible after randomization will be replaced if the ineligibility occurs while the study is still recruiting. If they become ineligible after the study recruitment period, their data will not be included in analyses.

Given the above scenario, an analysis sample of n=600 parent/child dyads (n=300 in each study arm) gives 84% power of detecting a significant decrease in caries incidence in the OHT vs. CWT group. This requires an enrollment sample of n=850 (n=425 in each study arm) to account for loss-to-follow-up.

If the underlying incidence of ECC is higher than the assumed 23.8% in the control CWT group, we will have greater power of detecting a difference between arms corresponding to an odds ratio of 0.53. For example, for an underlying incidence of ECC in the CWT group of 30%, the OR=0.53 corresponds to a difference in incidence of ECC of 18.6% vs 30% and a power of 90%. If the underlying incidence of ECC is lower in the CWT group, we will have lower power of detecting the OHT effect. For example, for an underlying incidence of ECC in the CWT group of 20%, the OR=0.53 corresponds to a difference in incidence of 11.8% vs 20% and a power of 0.78. If the underlying intervention effect is weaker than assumed, we will have lower power of detecting an effect. For example, with an incidence of ECC in the CWT group of 23.8% and an intervention effect corresponding to an odds ratio of 0.60 (incidence of 15.8% vs 23.8%) power would be 69%.

Power under different incidence levels and intervention effects, analysis samples of n=300 per study arm. The first row corresponds to our primary anticipated effect

OHT Effect Odds Ratio	ECC Incidence in CWT Group	ECC Incidence in OHT Group	Statistical Power
0.53	23.8%	14.3%	0.84
0.53	30.0%	18.6%	0.90
0.53	20.0%	11.8%	0.79
0.60	23.8%	15.8%	0.69
0.60	30.0%	20.4%	0.77

Justification of the anticipated OHT vs. CWT effects: Data from the behavioral interventions delivered by Kressin et al. (2009) and Weinstein et al. (2004) was used to calculate sample size and power because the Kressin oral health data was collected at the largest site in our study (BMC) and another pediatric clinic located within a teaching hospital 1 mile away (with a population comparable to that at our CHCs). In the study by Kressin, caries incidence in the control site was 31.7%; however, participants did not regularly receive fluoride varnish (FV), a known preventive measure which reduces caries risk. The application of FV is inconsistent and infrequent in our targeted CHCs, but if we conservatively assume that all child participants will receive the recommended 4 applications/year, then we can assume that the incidence of caries

among controls will be reduced an additional 25% (Weinstein et al, 2004) or from 31.7% to **23.8%**. Kressin et al. (2009) found a 44.2% reduction in caries incidence due to the brief patient centered counseling intervention during the pediatric well child visit. If we assume a similar effect from the daily text messaging intervention, we would expect a **13.3%** incidence of caries in the intervention group compared to 23.8% incidence in the control group (accounting for possible FV effect). To be slightly more conservative, we can use the 40% reduction in caries incidence found by Weinstein et al in his intervention and in the Marinho et al., 2013 Cochrane review. This would result in **14.3%** caries incidence for the intervention group. In this scenario, we would need 300 parent-child dyads at our 24 month follow-up to have an estimated 84% power (2 tailed) to detect a 9.5% difference in caries incidence between groups with alpha=0.05 and according to the standard chi-square test.

Our second primary hypothesis will examine the mechanism of the OHT effect, examining mediation through Social Cognitive Theory constructs of self-efficacy, motivation, and outcome expectations. Statistical power for tests of indirect effects of OHT through a mediator will be calculated using the joint effects approach; there is 80% power of detecting an indirect effect if the power of showing an association between OHT and the mediator, and an association between the mediator and 24 month caries incidence, are both 90%. We have 80% power of showing an indirect effect of a continuous mediator if intervention (OHT vs. CWT) explains 2% of the mediator ($R^2=.02$), and if a 1 standard deviation increase in the mediator leads to a 30% reduction in the odds of caries (an OR=0.70). This study was powered to detect an OHT effect in the overall sample. Secondary analyses examining whether the OHT effect varies across subpopulations defined by race/ethnicity, insurance coverage, maternal education level, or child's prior caries experience will have lower power. These analyses should therefore be considered exploratory.

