5.5.2 Handling of Subject Withdrawals or Subject Discontinuation of Study Intervention

We will attempt to obtain a final child oral health assessment and study questionnaires from all subject caregivers, including those who withdraw from the study for any reason. We will also attempt to perform an oral assessment on the child at the time of withdrawal if a subject withdraws early (before 24 months of participation). We will make a minimum of 5 attempts to contact the caregiver in cases of withdrawal and those who relocate. At the time of withdrawal, study staff will review procedures for contacting the study team in case an AE or UP occurs.

Once a participant has been randomized, and begins the program, replacement of that participant is not allowed if the participant withdraws prematurely. If the participant becomes ineligible (e.g., child no longer lives with them), then we will replace the subject but only if the study is within the specified recruitment period.

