12.4 Final Analysis Plan

Overview of Analytic Plan: Primary analyses will focus on the comparison of those assigned to OHT vs. CWT on oral health and behavior outcomes using all available data (i.e., restricted to those followed) and, following the intent-to-treat principle, randomized subjects will be included in the analysis regardless of their compliance with the study protocol and engagement in the study interventions. While no differences between study arms are anticipated due to randomization, preliminary analyses will explore differences between arms and variables found to differ between groups (at the $p<0.10$ level) will be adjusted for in analysis. For dichotomous outcome variables (e.g., incidence of any new caries at 24 months; use of fluoride toothpaste) analyses will use logistic regression models, with intervention effects reported as odds ratios

with 95% confidence intervals. Count data (e.g., number of new caries at 24 months) will be analyzed through Poisson regression models, if the distributional assumptions of the Poisson model are met, or negative binomial or zero-inflated models if the outcome distribution better meets the assumptions of these models. Results will be reported as rate ratios with 95% confidence intervals. Continuous variables (e.g., number of tooth brushings per week) will be analyzed through mixed effects linear regression models. Data will also be analyzed by race and gender as specified in the Notice of Grant Award, although these analyses will be exploratory due to lack of power. If follow-up falls below the anticipated 70%, primary analyses will account for missing data through inverse probability weighting using propensity scores for missingness. If follow-up meets the anticipated 70%, inverse probability weighting may be used in sensitivity analyses addressing the impact of missing data.

The two-tailed alpha 0.05 level will be used to indicate statistical significance.

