
Aims 2 and 3. We will compare changes in these behaviors over time in OHT vs. CWT using mixed effects logistic regression models (for dichotomous outcomes) and mixed effects linear regression models (for continuous outcomes). Changes in these behaviors from baseline to 2, 4, 12, and 24 months will be described through odds ratios and 95% confidence intervals for logistic models, and slopes for linear models. Differences in changes over time for OHT vs. CWT will be tested through group by time interaction terms.

Aim 4: To identify subpopulations for whom the intervention has the greatest effect, we will analyze moderators; e.g., race/ethnicity, insurance coverage, parent educational level, and child's prior caries experience. This aim focuses on moderator effects (also known as effect modification) for incident caries over 24 months. We will use logistic regression models with multiplicative interaction terms (treatment group x moderator) to compare the efficacy of OHT across subpopulations.

17. Missing data: We will gather follow-up information and reasons for dropout regardless of treatment completion, censoring at the point of loss. We will examine the extent of drop-out, and identify characteristics associated with drop-out through logistic regression. Given drop-out does not exceed the expected rate of 30%, primary analyses will be based on available data. Secondary analyses will account for missing data and explore the potential impact of drop-out on study findings. We will describe the robustness of our findings with respect to missing data using inverse probability weighting. This approach to handling missing data has two steps: 1) develop propensity scores for missing data, which involves using logistic regression to model the probability of being followed to the 24 month visit as a function of baseline variables, including history of caries; and 2) using the inverse of the propensity scores (predicted probabilities from the first step) to serve as weights in our logistic regression model of new

primary teeth caries. Provided the data are missing at random (MAR), that is, the probability of missingness can be fully explained by observable data, this approach produces asymptotically unbiased estimates. If there is sufficient missing data, and a concern that data may be missing not at random, we will also consider pattern mixture models to perform a sensitivity analysis of the potential impact of missingness.

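### Section 12.2 discards data already collected from dyads who become ineligible after recruitment closes; the final analysis plan in 12.4 carries no such exclusion (minor)

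*Combined protocol and SAP*

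**What the plan says.** Section 12.2 opens its treatment of the analysis sample with an intent-to-treat statement: "We will attempt to follow and include all parents in the analysis regardless of their compliance with the study protocol". It then makes an exception: "Participants, can, however, become ineligible after randomization (and not evaluable), for example, if a parent loses custody of the child". What follows depends on timing. During recruitment, "Participants who become ineligible after randomization will be replaced if the ineligibility occurs while the study is still recruiting". Afterwards, "If they become ineligible after the study recruitment period, their data will not be included in analyses". That last sentence is not limited to the 24-month outcome, or to data that would have been collected after the dyad became ineligible.

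Section 12.4 defines the primary analyses as "using all available data (i.e., restricted to those followed) and, following the intent-to-treat principle, randomized subjects will be included in the analysis". The only limit it states is being followed. Its missing-data text says: "We will gather follow-up information and reasons for dropout regardless of treatment completion, censoring at the point of loss". Neither passage mentions ineligibility.

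Section 5.5.2 seeks a final oral assessment and questionnaires "from all subject caregivers, including those who withdraw from the study for any reason". It provides for replacing ineligible dyads during recruitment but does not say what becomes of their data. Ineligibility is described only by example, in 5.5.2 and 12.2.

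**The concern.** Dropping a randomised dyad because of something that happened after randomisation is what an intent-to-treat analysis is meant to avoid. Here the rule sits in the sample-size section and is absent from the section that governs the analysis. An analyst following 12.2 would delete every record of a later-ineligible dyad. An analyst following 12.4 would keep whatever was collected.

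The records at stake are mostly not the 24-month exams:

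- **Primary aim 2.** Section 3.1 tests differential change in the Social Cognitive Theory constructs, using surveys at baseline and 2, 4, 12 and 24 months. Section 12.1 also traces indirect effects to new caries at 12 months.
- **Secondary aims 2 and 3.** Section 12.4 models change in behaviours from baseline to 2, 4, 12 and 24 months with mixed models, which can use partly observed dyads.
- **Primary aim 1.** The 24-month comparison loses a dyad only if the child was examined despite the ineligibility.

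**Working it through.** **1. The plan's own figure.** Inputs from 12.2: 23.8% (CWT) against 14.3% (OHT), 300 per arm, two-sided alpha 0.05, chi-square test. The odds ratio is (0.143/0.857)/(0.238/0.762) = 0.534. Power with pooled variance and no continuity correction is 0.844, against the stated 84%. The figure reproduces. The inflation to 850 enrolled is for loss to follow-up only; it contains no allowance for ineligibility.

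**2. Would data exist when the rule applies?** Section 4 gives about 1 year of enrolment and 2 years of participation. Assume even accrual and a constant rate of ineligibility, and ignore other attrition. A dyad enrolled at month u (uniform on 0 to 12) has 12 + u months of follow-up after recruitment closes.

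- Mean follow-up after closure: 12 + 6 = 18 of 24 months, or 75%.
- Part of it beyond the dyad's own month 12: 12 of 18 months, or 67%.
- Part of it beyond the dyad's own month 4: [∫₀⁸(12 + u)du + ∫₈¹² 20 du]/12 = (128 + 80)/12 = 17.33 of 18 months, or 96%.

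So, of dyads caught by the rule, about two thirds would be past the 12-month exam date and nearly all past the 4-month survey date. These shares say when the rule bites, not how many dyads it affects.

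**3. Effect on the 24-month comparison.** No ineligibility rate is given, so I assume that a share e of evaluable dyads is removed (2% or 5%, which is 6 or 15 of 300), with caries risk m times the average. The incidence among those left is p′ = p(1 − e·m)/(1 − e).

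One-arm bounding case: no true effect, p = 0.238, removal from OHT only, CWT kept at 300.

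| m | e | OHT n | p′ | OR | Type I error |
|---|---|---|---|---|---|
| 2 | 2% | 294 | 0.2331 | 0.973 | 5.2% |
| 2 | 5% | 285 | 0.2255 | 0.932 | 6.5% |
| 1.5 | 2% | 294 | 0.2356 | 0.987 | 5.1% |
| 1.5 | 5% | 285 | 0.2317 | 0.966 | 5.4% |
| 0.5 | 2% | 294 | 0.2404 | 1.013 | 5.1% |
| 0.5 | 5% | 285 | 0.2443 | 1.035 | 5.4% |

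If m = 1, or if e and m are equal in the two arms, the odds ratio under no effect stays at 1.00.

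Balanced removal under the design effect:

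| m | e | n per arm | OHT vs CWT | OR | Power |
|---|---|---|---|---|---|
| 1 | 2% | 294 | 14.30% vs 23.80% | 0.534 | 0.837 |
| 1 | 5% | 285 | 14.30% vs 23.80% | 0.534 | 0.825 |
| 2 | 2% | 294 | 14.01% vs 23.31% | 0.536 | 0.827 |
| 2 | 5% | 285 | 13.55% vs 22.55% | 0.538 | 0.799 |

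The effect of the rule on the mediator and behaviour models cannot be put into figures from the documents.

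**The case against.** The strongest reply is that 12.2 declares an exception openly, and that 12.4 is silent rather than contradictory. Its intent-to-treat promise is worded in terms of compliance and engagement, and its censoring sentence is about dropout. Section 12.2 also calls these participants not evaluable. A parent who has lost custody will usually have no 24-month exam to offer, and 12.4 already limits the primary analysis to those followed. For such a dyad both sections give the same primary analysis set. Likewise, its mediator surveys add nothing to the path from mediator to 24-month caries.

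Most of this stands, and it is why the point is minor. It does not rescue the sentence, which covers all of a dyad's data and every analysis. Being not evaluable at 24 months does not undo a 12-month exam or an earlier survey. Where no data exist, the sentence does nothing and can go at no cost.

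Two stronger readings are tempting. A reader might infer that the primary result is materially biased. The documents do not support that: nothing in them suggests that ineligibility depends on arm, and the group that is both ineligible and examined is probably small. A reader might also infer that the principal investigators, who are not blinded (5.4.2), could remove dyads through the best-interest withdrawal in 5.5. That is withdrawal, not ineligibility. No section drops the data of withdrawn subjects, and 5.5.2 seeks their final exam.

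**Conclusion.** The point holds as a minor one. Section 12.2 states a post-randomisation exclusion that reaches data already collected, and the final analysis plan does not carry it. The main consequence is the avoidable loss of 12-month exams and 2-, 4- and 12-month surveys for primary aim 2 and secondary aims 2 and 3. For the 24-month primary comparison the likely effect is small. It is nil under no true effect if removal is balanced or unrelated to outcome. Type I error reaches 6.5% only if 5% of evaluable dyads are removed from one arm at twice the average risk. Every removal rate and relative risk here is assumed, as are the even accrual and constant ineligibility rate behind the timing shares.

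**What to change.** - Delete the exclusion clause from 12.2.
- State in both 12.2 and 12.4 that every randomised dyad, including any that is replaced, stays in its randomised arm, and that every exam and survey obtained is used.
- State that an unobtained 24-month exam is missing data, handled under the missing-data plan already in 12.4.
- Define ineligibility, and use any exclusion for it only as a sensitivity analysis.

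The cost is a wording change, with no new visits or data. Reported missing 24-month outcomes may rise slightly, and if replacement is kept the number randomised may exceed 850 by the number replaced.

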12.3 Planned Interim Analyses (if applicable)

There is minimal risk associated with the interventions and no interim analysis are planned.

12.3.1 Safety Review

Safety concerns associated with this study are minimal and there are no plans to halt study enrollment in response to a Safety Review.

12.3.2 Efficacy Review

There is minimal risk associated with this study. No interim analyses are planned, and there are no plans to halt study enrollment in response to an efficacy review.

12.4 Final Analysis Plan

Overview of Analytic Plan: Primary analyses will focus on the comparison of those assigned to OHT vs. CWT on oral health and behavior outcomes using all available data (i.e., restricted to those followed) and, following the intent-to-treat principle, randomized subjects will be included in the analysis regardless of their compliance with the study protocol and engagement in the study interventions. While no differences between study arms are anticipated due to randomization, preliminary analyses will explore differences between arms and variables found to differ between groups (at the $p<0.10$ level) will be adjusted for in analysis. For dichotomous outcome variables (e.g., incidence of any new caries at 24 months; use of fluoride toothpaste) analyses will use logistic regression models, with intervention effects reported as odds ratios

with 95% confidence intervals. Count data (e.g., number of new caries at 24 months) will be analyzed through Poisson regression models, if the distributional assumptions of the Poisson model are met, or negative binomial or zero-inflated models if the outcome distribution better meets the assumptions of these models. Results will be reported as rate ratios with 95% confidence intervals. Continuous variables (e.g., number of tooth brushings per week) will be analyzed through mixed effects linear regression models. Data will also be analyzed by race and gender as specified in the Notice of Grant Award, although these analyses will be exploratory due to lack of power. If follow-up falls below the anticipated 70%, primary analyses will account for missing data through inverse probability weighting using propensity scores for missingness. If follow-up meets the anticipated 70%, inverse probability weighting may be used in sensitivity analyses addressing the impact of missing data.

The two-tailed alpha 0.05 level will be used to indicate statistical significance.

Primary aim 1: We will use logistic regression to compare the incidence of new caries in primary dentition (dmfs) over 24 months (no vs. any new caries) in OHT vs. CWT children, controlling for age, previous caries, and other relevant variables. Secondary analyses will also use logistic regression to compare OHT vs. CWT on the incidence of new caries in permanent dentition (DMFS) and mixed dentition (dmfs+DMFS). Secondary analyses of the number of new caries will be conducted using Poisson regression or related methods. Distributional assumptions of Poisson regression will be checked, and negative binomial regression models (for over-dispersion) and zero-inflated (negative binomial and Poisson) models (for excess zeros) will be considered if appropriate. Given that we are performing oral assessments at three time points (baseline, 12 and 24 months), we can also perform a tooth-level analysis of new caries in primary and permanent dentition, using mixed effects logistic regression models (Gibbons et al., 2010) to account for the multiple observations (teeth) per child.

Primary aim 2: Our second primary aim is to investigate the mechanisms of the OHT intervention effect on caries incidence (mediation analysis). Mediation analyses will examine indirect effects of OHT on caries incidence through constructs from Social Cognitive Theory (self-efficacy, motivation, and outcome expectations). We hypothesize that OHT will lead to improved self-efficacy, motivation, and outcome expectations, which in turn will be associated with better proximal outcomes (increased motivation and oral health behavior) at the end of treatment, 4 months. We further hypothesize that changes in mediators over the course of treatment will have a mediational effect on distal outcomes (change in oral health behaviors and lower caries incidence at 12 and 24 months). For descriptive analyses of mediation, we will take a causal steps approach and test individual mediators, as specified by MacKinnon and Fairchild (2007). Then, we will use the product of coefficients method, using bootstrapped confidence intervals (Shrout & Bolger, 2002) to account for the non-normality of the estimated indirect effect, which utilizes a multiple mediation model to simultaneously test the effects of potential mediators, and enabling the determination of the relative influence of each. We will also consider using a counterfactual approach (Valeri & Vanderweele, 2013) although it does not allow for time varying effects of mediators, and has not been previously used in oral health research like the MacKinnon procedure.

Secondary aims

Aim 1. We will conduct a Budget Impact Analysis (BIA) to assess the financial consequences of adoption, diffusion and sustainability of the OHT intervention. BIA will be undertaken from the perspective of the budget holder, who makes decisions regarding uptake of interventions. To do this, we will follow the best practice guidelines set forth by the International Society for Pharmacoeconomics and Outcomes Research (ISPOR) task force (Mauskopf et al., 2007). As such, we will identify detailed cost and claims data to assess the cost impact of providing the intervention and compare the clinical outcomes of the OHT intervention with the costs of achieving those outcomes, and conduct sensitivity analyses to present context specific scenarios for different situations (e.g., pediatric clinics that may have a lower/higher proportion of Medicaid patients). Sensitivity analysis will model two different strategies to incorporate the OHT intervention into routine clinical care: 1) a fully-automated strategy that involves an EHR prompt to providers recommending that they 'prescribe' the program to their patients and the system automatically enrolls the patient via an EHR to iSMILE and where a summary is returned to the EHR for guidance at future appointments; 2) a more labor intensive strategy but less technologically complex approach whereby the provider creates 'an order' in the EHR and a printout is initiated for the patient and the patient signs themselves up. We will be able to calculate the cost per caries prevented under each scenario. BIA is essential to helping potential diffusion targets to form business plans that determine the financial feasibility of the OHT intervention. We will survey IT specialists at all our sites as well as technical experts in industry to estimate interface and application costs. BIA is a useful approach to help stakeholder decision makers decide if this particular intervention is worth creating and sustaining beyond grant based startup funding. Policy decision makers will be able to plug in and alter assumptions as needed for their situations. We will explore whether or not it is possible to assess site specific effects using multilevel modeling (Charns et al., 2012). Interviews with decision makers from our currently targeted sites will be used to explore the barriers and facilitators to the intervention implementation and adoption. This will help develop plans for "implementation spread" to other sites that can be tailored to local requirements and needs.

Aims 2 and 3. We will compare changes in these behaviors over time in OHT vs. CWT using mixed effects logistic regression models (for dichotomous outcomes) and mixed effects linear regression models (for continuous outcomes). Changes in these behaviors from baseline to 2, 4, 12, and 24 months will be described through odds ratios and 95% confidence intervals for logistic models, and slopes for linear models. Differences in changes over time for OHT vs. CWT will be tested through group by time interaction terms.

Aim 4: To identify subpopulations for whom the intervention has the greatest effect, we will analyze moderators; e.g., race/ethnicity, insurance coverage, parent educational level, and child's prior caries experience. This aim focuses on moderator effects (also known as effect modification) for incident caries over 24 months. We will use logistic regression models with multiplicative interaction terms (treatment group x moderator) to compare the efficacy of OHT across subpopulations.

17. Missing data: We will gather follow-up information and reasons for dropout regardless of treatment completion, censoring at the point of loss. We will examine the extent of drop-out, and identify characteristics associated with drop-out through logistic regression. Given drop-out does not exceed the expected rate of 30%, primary analyses will be based on available data. Secondary analyses will account for missing data and explore the potential impact of drop-out on study findings. We will describe the robustness of our findings with respect to missing data using inverse probability weighting. This approach to handling missing data has two steps: 1) develop propensity scores for missing data, which involves using logistic regression to model the probability of being followed to the 24 month visit as a function of baseline variables, including history of caries; and 2) using the inverse of the propensity scores (predicted probabilities from the first step) to serve as weights in our logistic regression model of new

primary teeth caries. Provided the data are missing at random (MAR), that is, the probability of missingness can be fully explained by observable data, this approach produces asymptotically unbiased estimates. If there is sufficient missing data, and a concern that data may be missing not at random, we will also consider pattern mixture models to perform a sensitivity analysis of the potential impact of missingness.

